## 6. ANALYSES AND SUMMARIES

Refer to Section 4 for definitions of analysis sets and Section 5.2 for general methodology.

At the time of the SAP amendment 01 (SAP V2), the dose-finding phase had been completed and the only dose levels tested in the study will be DL1 and DL1 with lead-in. Therefore, no randomization will be implemented in the study.

Data will be summarized separately for DL1 and for DL1 with lead-in as well as for both treatment groups combined.

## 6.1. Primary Endpoints

### 6.1.1. DLT in Dose-finding Phase

#### 6.1.1.1. Primary analysis

The following analyses will be based on the DLT-evaluable set for patients in the dose-finding phase only. DLTs will be listed and summarized by treatment group.

## 6.2. Secondary Endpoint(s)

### 6.2.1. Safety endpoints

Refer to Section 6.6.

### 6.2.2. Efficacy endpoints

The following analyses will be based on the FAS by treatment group. Assessment of response by the Investigator will be made using RECIST v1.1.

#### 6.2.2.1. Objective response and tumor shrinkage from baseline

**Best overall response (BOR)** will be assessed based on reported overall lesion responses at different evaluation time points from the 'start date' until the first documentation of PD, according to the following rules. Only tumor assessments performed on or before the start date of any further anti-cancer therapies will be considered in the assessment of BOR. Clinical deterioration will not be considered as documentation of disease progression.

#### **BOR Based on Confirmed Responses:**

- CR = at least two determinations of CR at least 4 weeks apart and before first documentation of PD
- PR = at least two determinations of PR or better (PR followed by PR or PR followed by CR) at least 4 weeks apart and before first documentation of PD (and not qualifying for a CR)
- SD (applicable only to patients with measurable disease at baseline) = at least one SD assessment (or better)  $\geq$  6 weeks after the 'start date' and before first documentation of PD (and not qualifying for CR or PR).
- Non-CR/non-PD (applicable only to patients with non-measurable disease at baseline) = at least one non-CR/non-PD assessment (or better)  $\geq$  6 weeks after the 'start date' and before first documentation of PD (and not qualifying for CR or PR).
- PD = first documentation of PD  $\leq$  12 weeks after the 'start date' (and not qualifying for CR, PR, SD or non-CR/non-PD).
- NE: all other cases.

An objective status of PR or SD cannot follow one of CR. SD can follow PR only in the rare case that tumor increases by less than 20% from the nadir, but enough that a previously

documented 30% decrease from baseline no longer holds. If this occurs, the sequence PR-SD-PR is considered a confirmed PR. A sequence of PR – SD – SD – PD would be a best response of SD if the window for SD definition has been met.

**Objective Response (OR)** is defined as confirmed BOR of CR or PR according to RECIST v1.1.

Patients who do not have a post-baseline radiographic tumor assessment due to early progression, who receive anti-cancer therapies other than the study treatments prior to reaching a CR or PR, or who die, progress, or drop out for any reason prior to reaching a CR or PR will be counted as non-responders in the assessment of OR. Each patient will have an objective response status (0: no OR; 1: OR). OR rate (ORR) is the proportion of patients with OR in the analysis set.

ORR by treatment group will also be calculated along with the 2-sided 95% CI using the Clopper-Pearson method (exact CI for a binomial proportion as computed by default by the FREQ procedure using the EXACT option).

In addition, the frequency (number and percentage) of patients with BOR of CR, PR, SD, non-CR/non-PD (applicable only to patients with non-measurable disease at baseline), PD, and NE will be tabulated. Patients with BOR of NE will be summarized by reason for having NE status. The following reasons will be used:

- No baseline assessment
- No post-baseline assessments due to death
- No post-baseline assessments due to other reasons
- All post-baseline assessments have overall response NE
- New anti-cancer therapy started before first post-baseline assessment
- SD of insufficient duration (<6 weeks after the ‘start date’)
- PD too late (>12 weeks after the ‘start date’)

Special and rare cases where BOR is NE due to SD of insufficient duration and late PD will be classified as ‘SD of insufficient duration’.

Tumor shrinkage will be summarized as the percent change from baseline in target lesions (sum of longest diameter for non-nodal lesion and short axis for nodal lesion) per time point. It will be derived as:

- $((\text{Sum of target lesions at week XX} - \text{sum of target lesions at baseline}) / \text{sum of target lesions at baseline}) \times 100$

The maximum reduction in target lesions from baseline will be derived across all the post-baseline assessments until documented disease progression, excluding assessments after the start of subsequent anti-cancer therapy, as:

- Minimum of  $((\text{sum of target lesions at week XX} - \text{sum of target lesions at baseline}) / \text{sum of target lesions at baseline}) \times 100$

A waterfall plot of maximum percent reduction in the sum of longest diameter for non-nodal lesions and short axis for nodal lesions from baseline will be created by treatment group. These plots will display the best percentage change from baseline in the sum of the diameter of all target lesions for each patient with measurable disease at baseline and at least one post-baseline assessment.

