5.7.4. Concomitant Radiotherapy

Local radiotherapy (limited field) of isolated lesions with palliative intent is acceptable and allowed throughout the study (ie, starting from the screening through end of treatment) if considered medically necessary by the treating physician. All attempts should be made to rule out disease progression in the event of increased localized pain. If palliative radiotherapy is needed to control pain, the site(s) of disease causing pain should be present at baseline; otherwise, painful lesion(s) requiring radiotherapy will be considered as a sign of disease progression. The Medical Monitor should be consulted prior to starting radiotherapy and prior to restarting study treatment after the end of radiotherapy.

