- Complete Response (CR): Complete disappearance of all target lesions with the exception of nodal disease. All target nodes must decrease to normal size (short axis <10 mm). All target lesions must be assessed.
- Partial Response (PR): Greater than or equal to 30% decrease under baseline of the sum of diameters of all target measurable lesions. The short diameter is used in the sum for target nodes, while the longest diameter is used in the sum for all other target lesions. All target lesions must be assessed.
- Stable: Does not qualify for CR, PR or Progression. All target lesions must be assessed. Stable can follow PR only in the rare case that the sum increases by less than 20% from the nadir, but enough that a previously documented 30% decrease no longer holds.
- Objective Progression (PD): 20% increase in the sum of diameters of target measurable lesions above the smallest sum observed (over baseline if no decrease in the sum is observed during therapy), with a minimum absolute increase of 5 mm.
- Indeterminate. Progression has not been documented, and
 - One or more target measurable lesions have not been assessed;
or
 - Assessment methods used were inconsistent with those used at baseline;
or
 - One or more target lesions cannot be measured accurately (eg, poorly visible unless due to being too small to measure);
or
 - One or more target lesions were excised or irradiated and have not reappeared or increased.

Non-Target Disease

- CR: Disappearance of all non-target lesions and normalization of tumor marker levels. All lymph nodes must be 'normal' in size (<10 mm short axis).
- Non-CR/Non-PD: Persistence of any non-target lesions and/or tumor marker level above the normal limits.

090177e1907c3de0\0.1\Draft\Versioned On:01-Mar-2019 17:22 (GMT)

- PD: Unequivocal progression of pre-existing lesions. Generally the overall tumor burden must increase sufficiently to merit discontinuation of therapy. In the presence of SD or PR in target disease, progression due to unequivocal increase in non-target disease should be rare.
- Indeterminate: Progression has not been determined and one or more non-target sites were not assessed or assessment methods were inconsistent with those used at baseline.

New Lesions

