### **5.2.6. Definition of start of new anti-cancer therapy**

Start date of new anti-cancer therapy (drug, radiation, surgery) is used for censoring in efficacy analyses (see Section 6.2.2).

The start date of new anti-cancer therapy is the earliest date after the first dose of study treatment for the non-randomized phases or after the date of randomization for the randomized phase amongst the following:

- Start date of anti-cancer drug therapy recorded in the 'Follow-up Cancer Therapy' eCRF pages
- Start date of radiation therapy recorded in 'Concomitant Radiation Therapy', and 'Follow-up Radiation Therapy' eCRF pages with 'Treatment Intent' = 'Curative in intent'
- Surgery date recorded in 'Concomitant Surgery', and 'Follow-up Surgery' eCRF pages when 'Surgery Outcome' = 'Resected' or 'Partially Resected'.

When start date of anti-cancer therapy is missing or partially missing, the imputation rules described in Section 5.3.3.4 should be applied using 'Follow-up Cancer Therapy', 'Concomitant Radiation Therapy', 'Follow-up Radiation Therapy', 'Concomitant Surgery', and 'Follow-up Surgery' eCRF pages.

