### **5.2.11. Adequate post-baseline tumor assessment**

An adequate post-baseline assessment is defined as an assessment where a response of CR, PR, SD, non-CR/non-PD, or PD can be determined (see Section 6.2.2.1). Time points where the response is not evaluable (NE) or no assessment was performed will not be used for determining the censoring date.

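### The tumor-shrinkage summaries and waterfall plot keep scans taken after palliative irradiation of a target lesion, and give no rule for an incomplete target-lesion sum

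*SAP*

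**What the plan says.** **Shrinkage rule.** SAP 6.2.2.1 computes the percent change from baseline in the sum of target lesions at each time point. The maximum reduction is the minimum of these values, and it "will be derived across all the post-baseline assessments until documented disease progression, excluding assessments after the start of subsequent anti-cancer therapy". The waterfall plot then shows the best percent change "in the sum of the diameter of all target lesions for each patient with measurable disease at baseline and at least one post-baseline assessment". No other condition on the scan is stated.

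**What counts as new therapy.** SAP 5.2.6 defines the start of new anti-cancer therapy for the efficacy analyses. Radiation enters that definition only from "eCRF pages with 'Treatment Intent' = 'Curative in intent". Surgery enters when the outcome is resected or partially resected.

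**Radiotherapy on study.** Protocol 5.7.4: "Local radiotherapy (limited field) of isolated lesions with palliative intent is acceptable and allowed throughout the study". It makes no exception for target lesions.

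**Target response.** Protocol Appendix 2 makes target response Indeterminate, where progression has not been documented, in cases that include these two: "One or more target measurable lesions have not been assessed" and "One or more target lesions were excised or irradiated and have not reappeared or increased". CR, PR and stable disease each require that all target lesions be assessed.

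**Adequacy.** SAP 5.2.11 defines an adequate post-baseline assessment and states its use: "Time points where the response is not evaluable (NE) or no assessment was performed will not be used for determining the censoring date". The PFS and DR rules in Table 4 also rely on adequacy. The shrinkage rule does not mention it.

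**The concern.** The shrinkage derivation admits scans that the protocol's own response criteria treat as uninformative about the target lesions. Two kinds of scan are involved.

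- **Irradiated target lesion.** A lesion that shrinks under palliative radiation stays in the sum, and nothing in SAP 6.2.2.1 or 5.2.6 removes the scan. The bar then mixes radiation effect with the effect of avelumab plus axitinib. Protocol 7.6 applies the opposite principle at baseline, where a previously irradiated lesion may not be a target unless it has grown since.
- **Unmeasured target lesion.** The SAP does not say whether the sum is then missing or is taken over the remaining lesions.

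The direction matters more than the frequency. Adding scans to a minimum can deepen a bar or leave it alone; it can never make it shallower. Such errors do not average out across patients. SAP section 6 also presents DL1 with lead-in as a separate group. That group is likely to be small, so one affected bar would be visible.

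**Working it through.** The plan gives no figure for this point, so there is nothing to reproduce. The check applies the SAP formula, percent change = 100 x (sum at the scan - baseline sum) / baseline sum, to assumed lesion sizes. The documents give no sizes, no radiation effect and no rate of missing measurements. Appendix 2 caps target lesions at 5 in total.

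**Step 1. Does a scan after palliative irradiation stay in?**
- Palliative radiotherapy is permitted on treatment (protocol 5.7.4).
- It is not curative in intent, so it does not start new anti-cancer therapy (SAP 5.2.6).
- The scan is therefore not excluded by SAP 6.2.2.1 unless PD has been documented.
- Target response at that scan is Indeterminate until the irradiated lesion reappears or increases (Appendix 2).

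So the scan cannot support a response, yet it can set the patient's bar.

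**Step 2. Size when a target lesion is irradiated.**
- Targets 40, 30 and 20 mm, sum 90. The 40 mm lesion goes to 10 mm and the others are unchanged: sum 60, and 100 x (60 - 90)/90 = -33.3%.
- One of k equal lesions halves and the others are unchanged, giving -50/k: -50% (k = 1), -25% (k = 2), -16.7% (k = 3), -10% (k = 5).
- One of k equal lesions disappears, giving -100/k: -50% (k = 2), -33.3% (k = 3), -20% (k = 5).

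**Step 3. Size when a target lesion is unmeasured, only if the sum is taken over measured lesions.**
- Same targets, all truly unchanged. Without the 40 mm lesion: (50 - 90)/90 = -44.4%. Without the 20 mm lesion: (70 - 90)/90 = -22.2%.
- One of k equal lesions missing, giving -100/k: -50%, -33.3%, -25%, -20% for k = 2, 3, 4, 5.
- Targets 40, 30 and 30 mm, unchanged on three scans, one 30 mm lesion unmeasured on the second: the changes are 0%, -30%, 0%. The minimum over all scans is -30%; the minimum over complete scans is 0%.

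**Step 4. How often a scan might be incomplete.** Six-weekly imaging gives about 8 scans in the first year. With an assumed rate p of incomplete scans, independent across scans, the chance of at least one is 1 - (1 - p)^8: 7.7% for p = 1%, 21.6% for 3%, 33.7% for 5%. This is the chance of an incomplete scan. A false bar also needs partial summing and a value below the patient's true minimum.

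**The case against.** **A reader might infer that the SAP makes an unchanged tumor plot as a large reduction.** The documents do not support that as a stated rule. SAP 6.2.2.1 describes the plotted quantity as the sum over all target lesions, and SAP 5.3.1 bars imputation unless otherwise specified. A partial sum set against the full baseline sum in effect assigns 0 mm to the missing lesion, a value that Appendix 2 reserves for lesions considered to have disappeared. A natural reading is that the sum is then missing. What stands is that the SAP does not say so. In the radiation case the lesion really does shrink, so the error lies in attribution and the tumor is not unchanged.

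**Wording.** SAP 6.2.2.1 says subsequent therapy where 5.2.6 says new therapy, and SAP 6.5.5 lists radiation pages without an intent filter. But 5.2.6 is the start-date definition that the SAP assigns to the efficacy analyses, while 6.5.5 sets no start date. The radiation route therefore stands.

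**Rarity.** Protocol 5.7.4 limits such radiotherapy to isolated lesions and requires consultation with the Medical Monitor. Bone disease is non-measurable unless it has a measurable soft-tissue component. The frequency is unknown and may be low. However, 5.7.4 expects a painful irradiated site to have been present at baseline, so it may be a target.

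**Importance.** The primary endpoint is DLT, shrinkage is not among the endpoints in SAP 3.2.2, no formal testing is planned, and the expansion phase has no decision rules. This objection holds and limits the weight of the point.

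**Conclusion.** The point holds for palliative irradiation: under the rules as written, those scans stay in the minimum, and radiation shrinkage can be shown as drug effect. The illustration is -33% for one lesion going from 40 to 10 mm out of a 90 mm sum, and it rests on assumed sizes and an assumed radiation effect. For unmeasured lesions the point is an ambiguity. Bars of -20% to -50% for an unchanged tumor with 2 to 5 equal lesions arise only if the programming sums the measured lesions.

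The reach is limited to the per-time-point shrinkage summary, the maximum reduction and the waterfall plot. BOR, ORR, DR and PFS use overall responses, and under Appendix 2 such a scan is Indeterminate for them unless progression is documented. It would be wrong to infer that the response rate is inflated. Nor does a bar beyond -30% in a patient with BOR of SD prove this error, because an unconfirmed PR gives the same picture.

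**What to change.** Add to SAP 6.2.2.1, for the per-time-point percent change, the maximum reduction and the waterfall plot:

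- Compute percent change only at assessments where every baseline target lesion has a measurement, counting the 0 mm and 5 mm defaults of Appendix 2 as measurements. Otherwise set it to missing.
- Exclude assessments from the date a target lesion is irradiated, whatever the intent, unless that lesion has since increased, in line with Appendix 2.

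Excision needs little more, because resected and partially resected outcomes already count as new therapy under SAP 5.2.6.

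The cost is a sentence or two and a filter on lesion measurements and radiation pages that the SAP already uses. Irradiated sites must be matched to target lesions; the documents do not say whether the radiation page identifies the lesion, so a short medical review may be needed. A few scans, and occasionally a patient, will leave the plot; their number should be given in a footnote.

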#### **6.2.2.2. Disease control**

Disease Control (DC) is defined as BOR of CR, PR, non-CR/non-PD or SD. DC rate (DCR) is the proportion of patients with DC.

DCR will be summarized by frequency counts and percentages.

#### **6.2.2.3. Duration of response**

Duration of Response (DR) is defined, for patients with OR, as the time from the first documentation of objective response (CR or PR) to the date of first documentation of PD or death due to any cause. If a patient has not had an event (PD or death), DR is censored at the date of last adequate tumor assessment. The censoring rules for DR are as described for PFS in Table 4.

$$\text{DR (months)} = [\text{date of event or censoring} - \text{first date of OR} + 1] / 30.4375$$

Kaplan-Meier estimates (product-limit estimates) will be presented by treatment group together with a summary of associated statistics including the median DR time with 2-sided 95% CIs. In particular, the DR rate at 3, 6 and 12 months will be estimated with corresponding 2-sided 95% CIs. The CIs for the median will be calculated according to Brookmeyer and Crowley and the CIs for the survival function estimates at the time points defined above will be derived using the log-log transformation according to Kalbfleisch and Prentice (conftype=loglog default option in SAS Proc LIFETEST) with back transformation to a CI on the untransformed scale. The estimate of the standard error will be computed using Greenwood's formula.

DR will be displayed graphically and analyzed using Kaplan-Meier methodology. If the number of patients with OR is small, the Kaplan-Meier method may not provide reliable estimates. In this case, only descriptive statistics or listings will be provided.

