### **5.2.10. Adequate baseline tumor assessment**

Adequate baseline is defined using the following criteria:

- All baseline assessments must be within 31 days prior to and including the ‘start date’.
- All documented lesions must have non-missing assessments (ie, non-missing measurements for target lesions and non-missing lesions assessment status at baseline for non-target lesions).

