#### **6.2.2.5. Progression-free survival**

Progression-Free Survival (PFS) is defined as the time from the ‘start date’ to the date of the first documentation of PD or death due to any cause, whichever occurs first.

PFS data will be censored on the date of the last adequate tumor assessment for patients who do not have an event (PD or death), for patients who start a new anti-cancer therapy prior to an event (see Section 5.2.6) or for patients with an event after 2 or more missing tumor assessments. Patients who do not have an adequate baseline tumor assessment or who do not have an adequate post-baseline tumor assessment will be censored on the ‘start date’ unless death occurred on or before the time of the second planned tumor assessment (ie,  $\leq 12$  weeks after the ‘start date’) in which case the death will be considered an event.

In this study antitumor activity will be assessed through radiological tumor assessments conducted at screening and every 6 weeks until PD regardless of initiation of subsequent anti-cancer therapy. After 1 year from the ‘start date’, tumor assessments will be conducted less frequently, ie, at 12-week intervals.

The censoring and event date options to be considered for the PFS and DR analysis are presented in Table 4.

$$\text{PFS (months)} = [\text{date of event or censoring} - \text{‘start date’} + 1] / 30.4375$$

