**Table 4. Outcome and event dates for PFS and DR analyses**

Scenario	Date of event/censoring	Outcome
No adequate baseline assessment	‘Start date’	Censored a
PD or death - After at most one missing or inadequate post-baseline tumor assessment, OR - $\leq 12$ weeks after the ‘start date’	Date of PD or death	Event
PD or death - after 2 or more missing or inadequate post-baseline tumor assessments	Date of last adequate tumor assessment b documenting no PD before new anti-cancer therapy is given or missed tumor assessments	Censored
No PD and no death	Date of last adequate tumor assessment b documenting no PD before new anti-cancer therapy is given or missed tumor assessments	Censored
Treatment discontinuation due to ‘Disease progression’ without documented progression	Not applicable	Information is ignored. Outcome is derived based on documented progression only.
New anti-cancer therapy given	Date of last adequate tumor assessment b documenting no PD before new anti-cancer therapy is given or missed tumor assessments	Censored

a However if the patient dies  $\leq 12$  weeks after the ‘start date’ the death is an event with date on death date

b If there are no adequate post-baseline assessments prior to PD or death, then the time without adequate assessment should be measured from the ‘start date’; if the criteria were met the censoring will be on the ‘start date’.

Kaplan-Meier estimates (product-limit estimates) will be presented by treatment group together with a summary of associated statistics including the median PFS time with 2-sided 95% CIs. In particular, the PFS rate at 3, 6, 9, 12, 15, 18 and 24 months will be estimated with corresponding 2-sided 95% CIs. The CIs for the median will be calculated according to [Brookmeyer and Crowley](#) and the CIs for the survival function estimates at the time points defined above will be derived using the log-log transformation according to [Kalbfleisch and Prentice](#) (conftype=loglog default option in SAS Proc LIFETEST) with back transformation to a CI on the untransformed scale. The estimate of the standard error will be computed using Greenwood’s formula.

Frequency (number and percentage) of patients with each event type (PD or death) and censoring reasons will be presented by treatment group. Reasons for censoring will be summarized according to the categories in Table 5 following the hierarchy shown.

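### Duration of response borrows a PFS row that censors at the start date, so a confirmed responder with an inadequate baseline can get a negative duration while still counting in ORR

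*SAP*

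**What the plan says.** **DR.** SAP 6.2.2.3 measures DR in months from the first date of objective response to progression, death or censoring. For a patient without an event, "DR is censored at the date of last adequate tumor assessment". The next sentence reads "The censoring rules for DR are as described for PFS in Table 4". Protocol 9.4.1 likewise gives DR the PFS censoring rules.

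**Table 4.** Its title is "Outcome and event dates for PFS and DR analyses", so it is meant for both endpoints. Its first row, "No adequate baseline assessment", sets the date to the start date and the outcome to censored. Footnote a makes one exception: a death within 12 weeks of the start date is an event. SAP 6.2.2.5 repeats the rule for PFS, again with the start date as the censoring date and an exception for such early deaths: "Patients who do not have an adequate baseline tumor assessment or who do not have an adequate post-baseline tumor assessment will be censored on the" (…). The second row of Table 4 makes progression or death an event if at most one post-baseline assessment was missing or inadequate, or if it fell within 12 weeks of the start date.

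**Adequate baseline.** SAP 5.2.10 sets two conditions. The first is timing: "All baseline assessments must be within 31 days prior to and including the" start date. The second is completeness: every documented lesion, target or non-target, needs a recorded baseline assessment.

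**Response.** Under SAP 6.2.2.1, best overall response (BOR) "will be assessed based on reported overall lesion responses at different evaluation time points". Neither the list of patients counted as non-responders nor the reasons for a BOR of not evaluable (NE) mentions an inadequate baseline. The NE reasons name only the absence of a baseline.

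**The concern.** For PFS the start date is the time origin, so censoring there is harmless: the patient contributes one day. For DR the origin is first response, which comes later. The borrowed row therefore places the end of follow-up before its beginning.

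The protocol's own text does not create the problem. Protocol 9.4.1 sends patients to the start date when they have no baseline tumor assessment at all. In the SAP such a patient is NE and never enters the DR analysis. The SAP widened the trigger from no baseline to no adequate baseline and did not adjust OR or DR to match. A patient can now be a responder for ORR, be censored on day 1 for PFS, and have no usable value for DR.

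What is at stake is agreement between the ORR numerator and the set of patients in the DR curve, and whether the handling is fixed before the data are seen. DR is to be shown separately for DL1 and for DL1 with lead-in (SAP section 6) and by prognostic subgroup (SAP 6.4), so a single responder could be visible.

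**Working it through.** The plan states no figure on this point, so there is nothing of its own to reproduce. The check applies its formula and then asks whether such a patient can exist.

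**Inputs**
- DR (months) = (date of event or censoring - first date of OR + 1) / 30.4375 (SAP 6.2.2.3).
- Start date = first dose of study treatment (SAP section 2). No randomization will take place (SAP section 6).
- First scan 6 weeks after Cycle 1 Day 1, then every 6 weeks to 1 year (Protocol 7.6).
- With lead-in, the first dose is axitinib on Lead-in Day 1, about 7 days before Cycle 1 Day 1 (SAP 3.4.1, Protocol 3.1).

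**DR with censoring at the start date (day 0)**

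| First response | Calculation | DR (months) |
|---|---|---|
| Week 6, no lead-in | (0 - 42 + 1)/30.4375 | -1.35 |
| Week 12, no lead-in | (0 - 84 + 1)/30.4375 | -2.73 |
| Week 24, no lead-in | (0 - 168 + 1)/30.4375 | -5.49 |
| Week 6, with lead-in | (0 - 49 + 1)/30.4375 | -1.58 |
| Week 12, with lead-in | (0 - 91 + 1)/30.4375 | -2.96 |

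DR is zero if response falls one day after the start date and negative from the second day on. Every response at a scheduled scan is therefore affected.

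**The same patient under the competing rules.** Take first response at week 6 and a last adequate scan at week 48 (illustrative).
- No event, using the DR sentence in 6.2.2.3: (336 - 42 + 1)/30.4375 = 9.69 months, censored.
- Progression at week 48 with no missed scans, using the second row of Table 4: 9.69 months, event.
- Either case, using the first row of Table 4: -1.35 months, censored.
- Death on day 84, using footnote a: (84 - 42 + 1)/30.4375 = 1.41 months, event. This exception gives a sensible value.

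Table 4 gives no order of precedence between its rows. Table 5 ranks an inadequate baseline first, but only among PFS censoring reasons.

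**Can such a responder exist?**
- One non-target lesion without a baseline status, or one baseline scan taken too early, makes the baseline inadequate under 5.2.10.
- Protocol Table 9 allows an overall PR when non-target disease is indeterminate or missing, so a gap in a non-target lesion need not block a PR.
- An adequate post-baseline assessment (SAP 5.2.11) requires only that a response can be determined. It does not refer back to the baseline.
- No step of the BOR or OR derivation tests baseline adequacy.

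So the rules permit a confirmed responder with an inadequate baseline.

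**The case against.** The strongest reply is that the plan already keeps these patients out. Protocol Appendix 2 calls a baseline adequate only if all required scans fall within 28 days before treatment and all disease is documented. Otherwise, it says, later statuses should as a rule be indeterminate. That window is tighter than the SAP's 31 days, so a baseline that fails 5.2.10 also fails Appendix 2. If the investigator follows it, the patient ends as NE because no post-baseline assessment is evaluable. The schedule also fits the window: screening at most 28 days before enrollment plus treatment within 3 days makes 31. Breaching it takes a timing deviation. This stands as an argument that cases will be rare. It does not close the gap, because Appendix 2 hedges its rule and the SAP's response rules do not carry it over.

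A second reply is that a negative value is only one reading, and this is right. A reader might infer that DR must be impossible even when progression was documented on time. The documents do not support that: the second row of Table 4 fits the same patient and yields an event. Without a progression or death, the DR sentence in 6.2.2.3 yields a positive time. What can be said is that one stated rule gives an impossible value and that nothing ranks it against the others.

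Third, DR is secondary and descriptive. The SAP plans no formal hypothesis test and has no decision rule for the expansion phase. Protocol 9.4.1 lists the response, progression, death and last-assessment dates together, so an odd record would be noticed. That limits the harm, but noticing it after the data are in is not a prespecified rule.

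**Conclusion.** The point holds in a narrow form. Read literally, SAP 6.2.2.3 and the first row of Table 4 give a negative DR to a confirmed responder whose baseline exists but is inadequate: -1.35 months for a week-6 response without lead-in, -1.58 with it. The patient still counts in ORR. That row also conflicts with the preceding DR sentence when there is no event, and with the second row of Table 4 when progression is timely.

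This rests on two conditions: the baseline fails 5.2.10, and the investigator nonetheless reports a confirmed CR or PR despite Appendix 2. How many patients meet both cannot be derived from the documents, which give neither a rate of inadequate baselines nor a response rate among such patients. A reader might apply an assumed rate to the roughly 55 projected patients, but the result would be only the assumption restated. Nor do the documents say how negative times would be processed, so it cannot be claimed that such records would drop out of the Kaplan-Meier estimate or that the median DR would be biased. Footnote b of Table 4 causes no similar problem, because a confirmed responder has adequate post-baseline assessments.

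It is worth correcting before analysis, since it is a rule error in a reported endpoint. It does not touch the primary endpoint or any decision.

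**What to change.** Add to SAP 6.2.2.3, in substance: *for DR, the Table 4 row for patients without an adequate baseline, with its footnote a, does not apply; all other rows apply, including those for two or more missing or inadequate assessments and for new anti-cancer therapy; DR is never censored before the date of first response.*

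The middle clause matters. A looser sentence that simply made responders events at progression or death could be read as also removing the missed-assessment and new-therapy censoring that Protocol 9.4.1 gives to DR. The same progression could then be an event for DR and censored for PFS. Nothing is lost by dropping footnote a, because the second row of Table 4 already makes a death within 12 weeks an event. Footnote b needs no exemption.

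The alternative is to let baseline adequacy govern throughout: set BOR to NE in SAP 6.2.2.1 when the baseline is inadequate, and add that to the listed NE reasons. OR, DR and PFS then agree, in line with Appendix 2, but any such patient leaves the ORR numerator.

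Either choice costs a short SAP amendment and no new data. It should be made before the affected records are examined.
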